9.3.1. Adverse Events of Special Interest

AESIs include:

- Severe constipation (and/or severe, persistent, or worsening abdominal pain)
- Depression/other significant mood-related disturbance (active suicidal ideation or behavior, severe depressive and/or anxious symptoms, other severe psychiatric TEAE)
- Elevations in hepatic enzymes (see Appendix 3)
- Diarrhea (see Appendix 2)

9.3.2. Time Period and Frequency for Collecting Adverse Event, Adverse Events of Special Interest, Serious Adverse Event Information

All SAEs will be collected from the signing of the ICF until the Follow-Up Visit at the time points specified in the SoA (Section 1.3). All AEs will be collected from the first dose of IP.

Medical occurrences that begin before the start of IP but after obtaining informed consent will be recorded on the Medical History/Current Medical Conditions section of the eCRF not the AE section.

All SAEs will be recorded and reported to the Sponsor or designee immediately and under no circumstance should this exceed 24 hours, as indicated in Appendix 14. The Investigator will submit any updated SAE data to the Sponsor within 24 hours of it being available.

Adverse events of special interest must be reported to the Sponsor should they meet the definition of an SAE, and all timelines for reporting of SAEs should be adhered to.

Investigators are not obligated to actively seek AEs or SAEs after conclusion of study participation. However, if the Investigator learns of any SAE, including a death, at any time after a patient has been discharged from the study, and he/she considers the event to be reasonably related to the IP or study participation, the Investigator must promptly notify the Sponsor.

9.3.3. Method of Detecting Adverse Events, Adverse Events of Special Interest, and Serious Adverse Events

The method of recording, evaluating, and assessing causality of AEs and SAEs and the procedures for completing and transmitting SAE reports are provided in Appendix 14.

Care will be taken not to introduce bias when detecting AEs and/or SAEs. Open-ended and non-leading verbal questioning of the patient is the preferred method to inquire about AE occurrences.

9.3.4. Follow-up of Adverse Events, Adverse Events of Special Interest, and Serious Adverse Events

After the initial AE/SAE report, the Investigator is required to proactively follow each patient at subsequent visits/contacts. All SAEs, and non-serious AESIs (as defined in Section 9.3.1), will be followed until resolution, stabilization, the event is otherwise explained, or the patient is lost to follow up (as defined in Section 8.3). Further information on follow-up procedures is given in Appendix 14.

9.3.5. Regulatory Reporting Requirements for Serious Adverse Events

Prompt notification by the Investigator to the Sponsor of an SAE is essential so that legal obligations and ethical responsibilities towards the safety of patients and the safety of an IP under clinical investigation are met.

The Sponsor has a legal responsibility to notify both the local regulatory authority and other regulatory agencies about the safety of an IP under clinical investigation. The Sponsor will comply with country-specific regulatory requirements relating to safety reporting to the regulatory authority, IRBs/IECs, and investigators.

Investigator safety reports must be prepared for suspected unexpected serious adverse reactions (SUSARs) according to local regulatory requirements and Sponsor policy and forwarded to investigators as necessary.

An investigator who receives an investigator safety report describing an SAE or other specific safety information (e.g., summary or listing of SAEs) from the Sponsor will review and then file it along with the Investigator's Brochure and will notify the IRB/IEC, if appropriate, according to local requirements.

9.3.6. Pregnancy

Patients will be instructed that if they/their partner become pregnant during the study, this should be reported to the Investigator. The Investigator should also be notified of any pregnancy that occurs during the study but not confirmed until after completion of the study for at least 5 terminal half-lives (4 weeks) after the last dose. In the event that a patient/patient's partner is subsequently found to be pregnant after being included in the study, then consent will be sought from the partner and, if granted, any pregnancy will be followed, and the status of the mother and/or child will be reported to the Sponsor after delivery.

Clinical Study Protocol Altavant Sciences GmbH

Any patient reporting a pregnancy during the study will be discontinued from the IP. The patient will also be followed to determine the outcome of the pregnancy. Information on the status of the mother and child will be forwarded to the Sponsor. Generally, follow up will be no longer than 6 to 8 weeks following the estimated delivery date. Any premature termination of the pregnancy will be reported. Abnormal pregnancy outcomes (e.g., spontaneous abortion, fetal

Protocol RVT-1201-2002

Effective: 19JAN2022

If a pregnancy is reported, the Investigator should inform the Sponsor within 24 hours of learning of the pregnancy and should follow the procedures outlined in Appendix 4.

death, stillbirth, congenital anomalies, ectopic pregnancy) are considered SAEs.

9.4. Treatment of Overdose

Prior to this study, there has been no experience with rodatristat ethyl in patients with PAH. In healthy subjects, no safety concerns were identified following single doses ranging from 100 mg to 2000 mg or following repeat dosing over 14 days of up to 800 mg administered BID or up to 800 mg administered once daily (QD).

An overdose in this study is defined as a dose > 1200 mg on any single dosing occasion, or > 2400 mg in any 24-hour period.

Altavant Sciences GmbH does not recommend specific treatment for an overdose.

In the event of an overdose, the Investigator should:

- 1. Contact the Medical Monitor immediately
- 2. Closely monitor the patient for any AE/SAE and laboratory abnormalities as applicable
- 3. Obtain an unscheduled plasma sample for PK analysis if requested by the Medical Monitor (determined on a case-by-case basis)
- 4. Document the quantity of the excess dose as well as the duration of the overdose in the eCRF

Decisions regarding dose interruptions or modifications will be made by the Investigator in consultation with the Medical Monitor based on the clinical evaluation of the patient.

9.5. Pharmacokinetics

Blood samples for PK analysis of plasma rodatristat ethyl, rodatristat, M15 metabolite, selexipag, and ACT-333679 will be collected by indwelling cannula or venipuncture at the time points indicated in the SoA (Section 1.3). Note, selexipag/ACT-333679 PK samples will only be collected in subjects using selexipag at baseline. The actual date and time of each blood sample collection will be recorded.

Protocol RVT-1201-2002

Effective: 19JAN2022

The date and time of the dose of IP taken prior to the collection of each PK sample will be recorded and if the meal the dose was taken with was high in fat, should also be recorded.

Sample analysis will be performed under the control of the Sponsor. Plasma concentrations of rodatristat ethyl, rodatristat, M15, selexipag, and ACT-333679 will be determined using validated liquid chromatography-tandem mass spectrometry (LC-MS/MS) methods. Raw data will be archived at the bioanalytical site(s). Once the sample(s) has been analyzed for rodatristat ethyl, rodatristat, M15, selexipag, and ACT-333679, any remaining sample may be analyzed for other rodatristat-related metabolites and the results may be reported separately.

Samples will be collected into appropriate tubes as specified by the bioanalytical laboratory. Details of blood collection, processing, storage, and shipment will be provided in the laboratory manual.

Rodatristat ethyl and rodatristat concentration information that would unblind the study will not be reported to investigative sites or blinded personnel (including the Sponsor) until the study has been unblinded.

9.6. Pharmacodynamics

Blood samples for determination of plasma 5-HIAA will be collected by indwelling cannula or venipuncture at the time points indicated in the SoA in Section 1.3. The actual date and time of each blood sample collection will be recorded.

Urine samples will be collected for determination of 5-HIAA (bioanalytical lab) and urine creatinine (central laboratory; for determination of creatine corrected 5-HIAA concentration) at the time points indicated in the SoA in Section 1.3 and Section 1.4.

Sample analysis will be performed under the control of the Sponsor. Plasma and urine concentrations of 5-HIAA will be determined using a validated LC-MS/MS method. Raw data will be archived at the bioanalytical site.

Details of sample containers and processing will be contained in the laboratory manual.

10. STATISTICAL CONSIDERATIONS

A detailed description of statistical methods will be provided in a separate Statistical Analysis Plan (SAP) and the SAP will be finalized prior to database lock.

10.1. Statistical Hypotheses

No formal hypotheses are planned for the study.

10.2. **Sample Size Determination**

The sample size for this study was not based on a formal hypothesis testing. It is expected that 30 patients per arm will provide sufficient data to assess the safety and efficacy. Power calculations were conducted to examine the probability of detecting a difference among treatment groups for the percentage change of PVR from baseline.

A sample size of 90 patients with 30 patients to be randomized into 1 of the 3 treatment arms in a 1:1:1 randomization is planned. A sample size of 30 patients per arm will provide at least 80% power at a significance level of 0.05 (2-sided hypothesis) to detect a treatment difference of 0.75 times of standard deviation (SD) in the percentage change from baseline of PVR from baseline between an active arm and the placebo arm. If the SD for PVR percent change is 24%, the study has 80% power to detect a difference of 18% between an active arm and the placebo arm.

10.3. **Populations for Analyses**

For purposes of analysis, the following populations are defined:

Population	Description
Enrolled	All patients who sign the ICF
Intent-to-Treat (ITT)	All patients randomized into the study. For all summaries based on the ITT population, patients will be assigned to the treatment arm to which they were randomized.
Modified Intent-to-Treat (m-ITT):	All safety population patients that had an evaluable baseline and completed at least 1 post-baseline efficacy assessment. Patients will be analyzed according to the treatment they actually received.
Per Protocol (PP)	All m-ITT population patients who had no major protocol deviations and completed the Week 24 visit.
Safety	All patients randomly assigned to IP and who take at least 1 dose of IP. Patients will be analyzed according to the treatment they actually received.

10.4. Statistical Analyses

The SAP will be developed and finalized before database lock and will describe the patient populations to be included in the analyses and procedures for accounting for missing, unused, and spurious data. This section is a summary of the planned statistical analyses of the primary and secondary endpoints.

10.4.1. Efficacy Analyses

Endpoint	Statistical Analysis Methods
Primary	Primary efficacy analyses will be performed using the m-ITT and PP populations. Percent change from baseline in PVR will be analyzed using an analysis of covariance (ANCOVA) with Baseline PVR as the covariate. Additional baseline characteristics may also be evaluated as covariates in the model. The estimated between-treatment differences, 95% confidence intervals (CIs), and p-values will be presented. For patients who discontinue from the study early, the last-observation-carried-forward method will be used to impute the PVR at Week 24.
Secondary	Secondary efficacy analyses will be performed using the m-ITT and PP populations: Change in cardiac index, mPAP, mRAP, SvO2 at rest, and PAC from baseline to Week 24 TTCW Change in WHO FC Change in 6MWD from baseline Change in right atrial size & RV function: TAPSE, tricuspid annular systolic velocity, and RV fractional area change from baseline REVEAL Lite 2 score Change in PAH-SYMPACT from Baseline to Week 24 Change in 5-HIAA (plasma and spot urine concentration) The change from baseline to Week 24 endpoints will be analyzed using an ANCOVA model with treatment as a fixed effect, randomization stratum and baseline assessment as covariates. The estimated between-treatment differences, 95% CIs, and p-values will be presented. The change in 6MWD from baseline to Week 24 will also be compared between groups using non-parametric analysis of covariance within the framework of the extended Cochran-Mantel-Haenszel test. For endpoints measured over time, a mixed effect of repeated measure model may be used as sensitivity analyses. Details of statistical methods will be provided in the SAP. The time from the first dose of IP until to the first clinical worsening event will be summarized using Kaplan-Meier estimates and compared between treatment groups using the log-rank test.

Endpoint	Statistical Analysis Methods	
Exploratory	Will be described in the SAP finalized before database lock	

Protocol RVT-1201-2002

Effective: 19JAN2022

10.4.2. Safety Analyses

Safety and tolerability will be evaluated by assessment of AE incidence and changes in clinical laboratory tests, physical examinations, vital signs measurements, ECG readings, and suicidal ideation and behavior ratings at various time points during the study.

The following AE summaries will be generated:

- Adverse events
- Serious adverse events
- Adverse events leading to discontinuation
- Adverse events by severity
- Adverse events by relationship to the IP

AE verbatim text will be coded using the Medical Dictionary for Regulatory Activities (MedDRA). All AEs, both serious and nonserious, will be listed. AE summaries by treatment group and consisting of the number and percent of patients reporting each event at least once will be generated.

Clinical values will be listed for each patient and flagged high or low relative to the normal range where appropriate. Descriptive summary statistics will be created by treatment and visit.

Other safety data (e.g., physical examination) will be summarized descriptively by treatment and visit.

10.4.3. Other Analyses

Patient reported outcomes (HADS and QIDS-C), PK, PD, and exploratory descriptive analyses will be described in the SAP finalized before database lock. Population PK and any PK/PD analyses will be documented in a separate analysis plan and may be reported separately.

The planned analyses for the OLE portion of the study will be provided in the SAP.

10.5. Interim Analyses

An external, multidisciplinary, IDMC will review the progress of the study and perform interim reviews of unblinded safety data at regular intervals and provide recommendations to the Sponsor whether the nature, frequency, and severity of AEs and AESIs associated with IP warrant the early termination of the study in the best interests of the patients, whether the study should continue as planned, or whether the study should continue with modifications. The IDMC may also provide recommendations as needed regarding study design. While the IDMC will be asked to advise the Sponsor regarding future conduct of the study, including possible early study termination, the Sponsor retains final decision-making authority on all aspects of the study.

A separate SAP will describe the planned interim analyses in greater detail.

Clinical Study Protocol Altavant Sciences GmbH Protocol RVT-1201-2002 Effective: 19JAN2022

10.5.1. Independent Data Monitoring Committee

The primary role of the IDMC, which consists of independent physicians with experience in the care of patients with PAH and the conduct of randomized, controlled studies and one non-voting biostatistician, is to ensure the safety of the patients enrolled in the study, including the OLE. Details of the IDMC's specific activities will be defined by a mutually agreed charter, which will define the IDMC's membership, conduct and meeting schedule. This charter will be maintained by the Sponsor or designee.

APPENDIX 1. CONCOMITANT AND PROHIBITED MEDICATIONS

NARROW THERAPEUTIC RANGE SUBSTRATES OF CYTOCHROME P450 (CYP)2C8, CYP3A, AND P-GLYCOPROTEIN (P-GP) Patients using the following systemic narrow therapeutic range substrates of CYP2C8, CYP3A and P-gp are allowed but should be monitored during coadministration with IP.

Protocol RVT-1201-2002

Effective: 19JAN2022

CYP2C8	Trepostinil
C112C0	 
	Selexipag
	Torasemide
	Trimethoprim
	Gemfibrozil
	Rosiglitazone
	Pioglitazone
CYP3A	Alfentanil
	Cyclosporine
	(dihydro)ergotamine
	Everolimus
	Fentanyl
	Sirolimus
	Tacrolimus
P-gp	Digoxin
	Dabigatran
	Fexofenadine

PROHIBITED MEDICATIONS

The following medications should not be used during the study:

Class	Drug Name Generic Name
Monoamine Oxidase Inhibitors (MAOIs)	Isocarboxazid Phenelzine Selegiline Tranylcypromine
Tryptophan Hydroxylase Inhibitor	Telotristat Ethyl
Marketed drugs known to prolong QT/QTc AND which are also clearly associated with a known risk of Torsades de Pointe source: www.CredibleMeds.org (Woosley, 2021)	Amiodarone (Cordarone and others) Anagrelide (Agrylin and others) Arsenic trioxide (Trisenox) Astemizole (Hismanal Azithromycin (Zithromax and others Bepridil (Vascor) Chloroquine (Aralen)

Altavant Sciences GmbH	Effective: 19JAN2022
Class	Drug Name Generic Name
	Chlorpromazine (Thorazine and others)
	Chlorprothixene (Truxal)
	Cilostazol (Pletal)
	Ciprofloxacin (Cipro and others)
	Cisapride (Propulsid)
	Citalopram (Celexa and others)
	Clarithromycin (Biaxin and others)
	Cocaine (Cocaine)
	Disopyramide (Norpace)
	Dofetilide (Tikosyn)
	Domperidone (Motilium and others)
	Donepezil (Aricept)
	Dronedarone (Multaq)
	Droperidol (Inapsine and others)
	Erythromycin (E.E.S. and others)
	Escitalopram (Cipralex and others)
	Flecainide (Tambocor and others)
	Fluconazole (Diflucan and others)
	Gatifloxacin (Tequin)
	Grepafloxacin (Raxar)
	Halofantrine (Halfan)
	Haloperidol (Haldol and others)
	Hydroxychloroquine (Plaquenil and others)
	Ibogaine
	Ibutilide (Corvert)
	Levofloxacin (Levaquin and others)
	Levomepromazine/methotrimeprazine (Nosinan and others)
	Levomethadyl acetate (Orlaam)
	Levosulpiride (Lesuride and others)
	Mesoridazine (Serentil)
	Methadone (Dolophine and others)
	Moxifloxacin (Aveloxand others)
	Ondansetron (Zofran and others)
	Oxaliplatin (Eloxatin)
	Papaverine HCl Intracoronary

Protocol RVT-1201-2002

Class	Drug Name
	Generic Name
	Pentamidine (Pentam)
	Pimozide (Orap)
	Probucol (Lorelco)
	Procainamide (Pronestyl and others)
	Propofol (Diprivan and others)
	Quinidine (Quinaglute and others)
	Roxithromycin (Rulide and others)
	Sertindole (Serdolect and others)
	Sevoflurane (Ultane and others)
	Sotalol (Betapace and others)
	Sparfloxacin (Zagam)
	Sulpiride (Dogmatil and others)
	Sultopride (Barnetil and others)
	Terfenadine (Seldane)
	Terlipressin (Teripress and others)
	Terodiline (Micturin and others)
	Thioridazine (Mellaril and others)
	Vandetanib (Caprelsa)

Protocol RVT-1201-2002 Effective: 19JAN2022

APPENDIX 2. DIARRHEA MANAGEMENT

CTCAE Grade	Description	IP	Symptom/Treatment
Mild = 1 (uncomplicated)	Increase of < 4 stools per day over Baseline	Continue same dose	Consider anti-diarrheal medicines e.g., 4 mg loperamide followed by 2 mg after each loose stool
			or every 2-4 hours to a maximum of 16 mg/day until bowel movements cease for 12 hours
Moderate = 2	Increase of 4–6 stools	If Grade 2 diarrhea	Continue anti-diarrheal
(uncomplicated)	per day over Baseline;	persists for ≥ 48 hours, IP should be	medicines, if Grade 2 persists for ≥ 48 hours assess
	IV fluids indicated < 24 hours;	interrupted until recovered to Grade ≤ 1	for dehydration and electrolyte imbalance,
	< 24 Hours,	followed by dose	consider IV fluids and
	Not interfering with ADL	reduction.	electrolyte replacement as clinically indicated.
		Dose re-escalation is possible within 4 weeks	
		after start of reduced dose.	
Severe = 3	Increase of ≥ 7 stools	IP interruption until	See Grade 2.
(complicated)	per day over Baseline;	recovery to Grade ≤ 1 followed by dose	Consider stool cultures and
	Incontinence;	reduction.	clostridium botulinum toxins to exclude any infection;
	IV fluids \geq 24 hours;	In case of recurrence of Grade 3 diarrhea despite	aggressive IV fluid replacement ≥ 24 hours,
	Hospitalization;	optimal symptomatic treatment and dose	hospitalization as clinically indicated, consider referral
	Interfering with ADL	reduction, IP should be permanently discontinued.	to a GI specialist to rule out potential differential diagnoses.
Life-threatening =	Life-threatening	See Grade 3.	See Grade 3.
4	consequences	200 31000 31	200 21440 21
(complicated)	(e.g., haemodynamic collapse)		

Protocol RVT-1201-2002

Effective: 19JAN2022

Abbreviations: ADL = activities of daily life; CTCAE = Common Terminology Criteria for Adverse Events; GI = gastrointestinal; IP = investigational product; IV = intravenous

APPENDIX 3. LIVER SAFETY: SUGGESTED ACTIONS AND FOLLOW-UP ASSESSMENTS

Protocol RVT-1201-2002

CTCAE Grade	Description	IP	Symptom/treatment
Mild = 1	AST or ALT > 1.5X ULN < 3X ULN	Continue as planned	No action taken
Moderate = 2	AST or ALT ≥ 3X ULN and < 5X ULN and no signs of severe liver damage	Reduce to one pill BID or interrupt treatment (to be decided by Investigator, based on individual risk assessment.)	Re-test ALT and AST, as well as ALP, TBL, and eosinophils within 48-72 hours, then at ~7 days, then at ~2 weeks, and assess for signs of severe liver damage: If AST and ALT < 3X ULN after 2 weeks, return to initial dose if reduced, restart at reduced dose if interrupted. Monitor labs (see above) every 2 weeks for at least 8 weeks. If AST and ALT ≥ 3X ULN after 2 weeks or anytime thereafter, permanently discontinue study medication.
Severe = 3	AST or ALT increase to ≥ 5X ULN and < 8X ULN and no signs of severe liver damage	Interrupt treatment	Re-test ALT and AST, as well as ALP, TBL, and eosinophils within 48-72 hours, then at ~7 days, then at ~2 weeks, and assess for signs of severe liver damage: • If AST and ALT < 3X ULN after 2 weeks, restart at reduced dose. Monitor labs (see above) every week for 4 weeks, then

Protocol RVT-1201-2002 Effective: 19JAN2022

CTCAE Grade	Description	IP	Symptom/treatment
			every 2 weeks for at least 8 weeks.
			• If AST and ALT ≥ 3X ULN after 2 weeks or anytime thereafter, permanently discontinue study medication.
Life-threatening = 4	AST or ALT increase to ≥ 8X ULN or signs of severe liver damage:	Permanently Discontinue	Patients showing these laboratory abnormalities need to be followed up
	-Increase of liver transaminases (ALT or AST ≥ 3X ULN)		closely
	and		
	Appearance of fatigue, nausea, vomiting, right upper abdominal quadrant pain or tenderness, fever, rash and/or eosinophilia (> 5%)		
	or		
	TBL > 1.5X ULN		
	or		
	INR > 1.5		

Abbreviations: ALP = alkaline phosphatase; ALT = alanine aminotransferase; AST = aspartate aminotransferase; BID = twice daily; CTCAE = Common Terminology Criteria for Adverse Events; INR = international normalized ratio; IP = investigational product; ULN = upper limit of normal

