4.4.1.2. Aminotransferase (Alanine aminotransferase or Aspartate Aminotransferase) Elevation

Management recommendations for ALT or AST elevations are based on U.S. Food and Drug Administration (FDA) Guidance for Liver Toxicity.

In general, all baseline or treatment-emergent ALT or AST elevations > 3X ULN should be confirmed within 48 to 72 hours with repeat assessments of ALT and AST as well as TBL, alkaline phosphatase (ALP), prothrombin time/INR, and complete blood count for eosinophil levels. Further details for managing IP reduction, restart, and discontinuation can be found in Appendix 3.

If at any time, the criteria as outlined in Section 8 are met, the IP must be permanently discontinued.

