8.1. Discontinuation of Investigational Product

The Medical Monitor should be notified of any change to background PAH therapy to determine any need for withdrawal. See Section 8.2 for study withdrawal procedures.

Patients meeting any of the following liver chemistry criteria must be withdrawn (IP should be discontinued immediately) from the study by the Investigator:

- ALT or AST > 3X ULN and TBL > 1.5X ULN or INR > 1.5
- ALT or AST > 3X ULN with the appearance of fatigue, nausea, vomiting, right upper quadrant pain or tenderness, fever, rash, and/or eosinophilia (> 5%)
- ALT or AST > 5X ULN for more than 2 weeks
- ALT or AST >8X ULN

If liver chemistry tests meet any of the above criteria, repeat testing should be performed within 48 to 72 hours and the patient followed until resolution.

Patients meeting any of the following confirmed QT/QTc-related criteria must be withdrawn from the study by the Investigator:

- QTcF interval > 500 ms
- QTcF interval > 480 ms AND increase from Baseline ≥ 60 ms
- QTcF interval > 480 ms associated with syncope, life-threatening arrhythmias, resuscitated cardiac arrest, or seizure

The Investigator must also discontinue/withdraw a patient's participation in the study if any of the following criteria apply:

- Pregnancy
- Significant protocol violation/lack of compliance with the study and/or study procedures non-compliance with IP for discontinuation of patient is defined as < 50%.
- Severe constipation (e.g., obstipation with manual evacuation indicated) and/or severe, persistent, or worsening abdominal pain
- Any significant worsening on postdose C-SSRS indicative of active suicidal ideation with intent to act (defined as C-SSRS Suicidal Ideation category score of 4 or 5) or behavior (either preparatory acts/behavior, aborted attempt, interrupted attempt, or actual attempt)
- Severe depression or anxiety based on a HADS Depression or Anxiety score ≥ 15, or a QIDS-C Total Score ≥ 16.

• Any severe psychiatric or CNS AE as determined by the Investigator.

The Investigator may discontinue/withdraw a study patient's participation in the study if any of the following criteria apply:

Protocol RVT-1201-2002

Effective: 19JAN2022

• Behavioral or administrative reason

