Any clinical AE, laboratory abnormality, or other medical condition or situation occurs such that continued participation in the study would not be in the best interest of the patient. When applicable, patients should be informed of circumstances under which their participation may be terminated by the Investigator without their consent.

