9. STUDY ASSESSMENTS AND PROCEDURES

Study procedures and their timing are summarized in the SoA in Section 1.3 for the Main Study and in Section 1.4 and Section 1.5 for the OLE.

Safety concerns should be discussed with the Sponsor immediately upon occurrence or awareness to determine if the patient should continue or discontinue IP.

Adherence to the study design requirements, including those specified in the SoA, is essential and required for study conduct.

All screening evaluations must be completed and reviewed to confirm that potential patients meet all eligibility criteria. The Investigator will maintain a screening log to record details of all patients screened and to confirm eligibility or record reasons for screening failure, as applicable.

Once all screening procedures are complete and the Investigator determines that the patient is eligible, the site must upload/send the required supporting documentation for approval by the Sponsor. The required information will include the RHC report (including tracings), PFTs obtained (may use PFTs completed in the 24 week period prior to screening or obtained at Screening), the screening echocardiogram, as well as specific information about the patient's medical history and disease state to further ensure the appropriateness of each patient being enrolled into this study. Approval from the Sponsor must be obtained prior to randomization.

All assessments should be completed predose unless otherwise stated.

If assessments are scheduled for the same nominal time, then the assessments should occur in the following order whenever possible: ECGs, vital signs, safety blood draws, PK blood draws.

Note: The timing of the assessments should allow the blood draw to occur as close as possible to the nominal time but before dosing.

Repeat or unscheduled samples may be taken for safety reasons or due to technical issues with the initial samples.

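### Appendix 3's permanent liver stop needs both AST and ALT at 3X ULN or above, so a persistent, isolated, asymptomatic elevation of 3X to 5X ULN has no mandated stop

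*Protocol*

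**What the plan says.** Protocol Section 4.4.1.2 refers sites to Appendix 3 for liver-related dosing decisions: "Further details for managing IP reduction, restart, and discontinuation can be found in Appendix 3".

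In Appendix 3 the Grade 2 row is entered on "AST or ALT ≥ 3X ULN and < 5X ULN and no signs of severe liver damage". The action is "Reduce to one pill BID or interrupt treatment (to be decided by Investigator, based on individual risk assessment", so the patient may remain on drug. The Grade 3 row is also entered on either enzyme, from 5X to below 8X ULN, and treatment is interrupted. Both rows call for re-tests at 48 to 72 hours, about 7 days and about 2 weeks, followed by two branches.

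- Resume (Grade 2 wording): "If AST and ALT < 3X ULN after 2 weeks, return to initial dose if reduced, restart at reduced dose if interrupted". The Grade 3 row uses the same two-enzyme condition and restarts at the reduced dose.
- Stop (both rows): "If AST and ALT ≥ 3X ULN after 2 weeks or anytime thereafter, permanently discontinue study medication".

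The Grade 4 row stops treatment if either enzyme reaches 8X ULN, or if either is at least 3X ULN with listed symptoms, eosinophilia, raised bilirubin or raised INR.

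Section 8.1 requires withdrawal for either enzyme above 3X ULN with raised bilirubin or INR, above 3X with symptoms or eosinophilia, above 8X, or on duration: "ALT or AST > 5X ULN for more than 2 weeks". Section 2.3 has the same structure with a higher bilirubin limit.

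**The concern.** The two branches should between them cover every patient in the row. The resume condition is that both enzymes are below 3X ULN, and its complement is that at least one is at or above 3X. The stop sentence instead requires both to be at or above 3X. A patient with one enzyme raised and the other below 3X falls between the branches, although the row's own entry rule admits that pattern.

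This is a patient-safety matter. Hepatic enzyme elevation is a named risk in Section 2.3 and an adverse event of special interest in Section 9.3.1. For this pattern, whether the patient stays on drug is decided case by case, and two sites could act differently on the same result.

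**Working it through.** The plan states no figure on this point, so the check is of rule logic.

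**Inputs.** Entry, resume, stop and Grade 4 conditions from Appendix 3; withdrawal criteria from Sections 8.1 and 2.3. Scenario: re-test after 2 weeks, no symptoms, normal bilirubin, INR and eosinophils.

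**Step 1: rules as written.** Split each enzyme into four bands, giving 4 × 4 = 16 states (ALT in rows, AST in columns, multiples of ULN).

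| | < 3 | 3 to < 5 | 5 to < 8 | ≥ 8 |
|---|---|---|---|---|
| **< 3** | resume | neither | neither* | Grade 4 stop |
| **3 to < 5** | neither | Appendix 3 stop | Appendix 3 stop | Grade 4 stop |
| **5 to < 8** | neither* | Appendix 3 stop | Appendix 3 stop | Grade 4 stop |
| **≥ 8** | Grade 4 stop | Grade 4 stop | Grade 4 stop | Grade 4 stop |

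Count: 1 resume + 4 Appendix 3 stops + 7 Grade 4 stops + 4 neither = 16.

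**Step 2: apply Section 8.1.** The two starred states have drug held under the Grade 3 row and must be withdrawn once the value has been above 5X for more than 2 weeks. The two isolated 3 to < 5X states meet no criterion in Section 8.1 or 2.3.

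**Step 3: finer grid.** Twelve values per enzyme from 1X to 9X ULN, same scenario and more than 2 weeks from onset. States with at least one enzyme ≥ 3X and no mandated stop: 3 values below 3X (1, 2, 2.9) × 5 values from 3X to 5X (3, 3.5, 4, 4.9, 5) × 2 orderings = 30. All have exactly one enzyme at 3X to 5X and the other below 3X.

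**Step 4: stop on either enzyme.** The 16 states become 1 resume + 8 Appendix 3 stops + 7 Grade 4 stops + 0 neither. On the finer grid, the 30 states fall to 0.

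These counts test whether the rules are complete. They are not risk weights.

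**Step 5: what happens to the patient.** Take ALT 4X, AST 2X ULN. If the dose was reduced, it cannot return to the initial level, but nothing in Appendix 3 ends the reduced dosing. If treatment was interrupted, it cannot restart, but no final outcome is stated. If the elevation resolves, dosing resumes and the isolated elevation then recurs, the patient re-enters the Grade 2 row and is again reduced or interrupted.

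**Step 6: size.** The only clinical ALT data in the documents (Section 4.7) are mild, transient elevations in 5 of 136 subjects, 5/136 = 3.7%, with no ULN multiple. That gives no rate for a persistent isolated elevation of at least 3X, so no expected count is offered.

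**The case against.** The strongest objection is that the patient is well covered by other provisions. Much of this stands:

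- Neither re-escalation nor restart is possible while either enzyme is at or above 3X.
- Section 4.4.1 describes reductions as temporary and asks for discussion with the Medical Monitor beforehand where safety allows.
- Section 9.2.5.5 asks for clinically significant laboratory abnormalities to be repeated until normal, back to baseline or no longer significant. If they do not settle in reasonable time, the cause is to be identified and the Sponsor told.
- Section 9 says "Safety concerns should be discussed with the Sponsor immediately upon occurrence or awareness to determine if the patient should continue or discontinue IP".
- Sections 9.3.1 and 9.3.4 require follow-up of hepatic events to resolution or stabilization.
- Section 8.1 lets the investigator withdraw a patient if "Any clinical AE, laboratory abnormality, or other medical condition or situation occurs such that continued participation in the study would not be" in the patient's best interest.

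A reader might infer that the patient goes unmonitored until the next scheduled laboratory visit. The documents do not support that, because Section 9.2.5.5 calls for repeat testing outside the schedule. A reader might also infer that a recurrence is unhandled. It is handled by re-entry to the Grade 2 row with its re-tests, but it lacks a mandated stop. None of these provisions requires treatment to end.

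A second objection is that the two-enzyme threshold may be deliberate: Sections 2.3 and 8.1 do not stop for an isolated asymptomatic 3X to 5X value, and Appendix 3 is titled as suggested actions. This is weak. Every other liver stop in the protocol works on either enzyme, the Appendix 3 sentence is directive, and Section 4.4.1.2 relies on the appendix for discontinuation. A deliberate threshold would also need a third instruction for one raised enzyme, and there is none. A drafting slip is the likelier explanation.

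**Conclusion.** The gap is real on the literal text and narrow: one enzyme at 3X to 5X ULN, the other below 3X, no symptoms, normal bilirubin, INR and eosinophils, persisting after 2 weeks or recurring later. For that patient no stop is mandated, and a Grade 2 patient on reduced dose may stay on drug at discretion.

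This is a minor patient-safety correction, worth making because it is cheap. The numbers are probably small, but the documents do not allow an estimate. Any assumed rate would be speculative, since even the 3.7% in Section 4.7 counts all reported mild ALT elevations. A reader might infer an effect on the PVR analysis; nothing in the documents supports one, and none is claimed.

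The conclusion assumes that *and* in the stop sentence means both enzymes, as it does in the adjacent resume sentence.

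**What to change.** In the Grade 2 and Grade 3 rows of Appendix 3, change *and* to *or* between the enzymes in the stop sentence, so that AST or ALT at or above 3X ULN after 2 weeks or at any later time means permanent discontinuation. Leave the resume sentence as it is. The two branches are then exact complements.

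The change needs no new tests, because AST and ALT are already re-tested together. Under the new wording a single later isolated value could trigger the stop; the 48 to 72 hour repeat already in Section 4.4.1.2 can serve as confirmation.

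The cost is possibly a very few more permanent discontinuations. Each may lose eligibility for the open-label extension, which Section 7.4 and the Main Study schedule of assessments reserve for patients who do not discontinue early and who complete through Week 24. If the Week 24 catheterization is also missed for tolerability, SAP Section 7.1.2.2 imputes PVR as the worst value in the arm. That is not automatic, since Section 8.2.1 keeps willing patients on visits through Week 24. The Treatment Completer set loses no one, because the earlier reduction or interruption already excludes the patient.
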